4.2 Scientific Rationale for Study Design

Heart disease is the leading cause of death for both men and women in the United States and worldwide (Mercado et al 2015). Elevated cholesterol is a key risk factor for heart disease, and while lowering cholesterol with statin drugs reduces cardiovascular morbidity and mortality, only about half of the people in the United States who require therapy are currently being treated (Mercado et al 2015). This represents a substantial public health issue for the United States. There are numerous reasons why people are not treated, but what is clear is that easier access to safe, effective, and affordable therapy would have a significant positive impact on public health. One way to simplify access to statin therapy would be to make it available to consumers without a prescription (e.g., OTC). Past attempts to achieve an OTC switch for statin treatment have failed due to concerns about the efficacy of the statins that were tested, and because consumers were unable to properly self-select. The Crestor OTC program addresses these two concerns by using Crestor 5 mg (a safe and highly effective dose of rosuvastatin with minimal interactions) and a TASS tool that ensures the medicine is only made available to consumers for whom it is appropriate (AstraZeneca Pharmaceuticals LP 2021). Completed studies evaluating DFL comprehension, CIL comprehension, Web App comprehension, Human Factors, Targeted Self-Selection and All-comers Self-Selection have shown that this approach is viable. Based on the success of these non-interventional behavioral studies, AstraZeneca is ready to proceed with the AUS.

The AUS is designed to test the ability of participants to input their medical data into a Web App in order to get a correct TASS outcome for the initial purchase as well as to assess their ability to correctly enter their ongoing health status into the Web App to demonstrate proper use of nonprescription rosuvastatin during the use period. Nonprescription rosuvastatin will only be available online for purchase via the Web App and direct shipment to the participant. It is intended for use by:

- Males 20-39 years of age with high LDL-C (160-189 mg/dL) plus family history of cardiovascular disease (CVD) (mother/sister younger than 65 years of age or father/brother younger than 55 years of age)
- Females 50-75 years of age with ASCVD risk score between 7.5% - <20% and LDL-C 70-189 mg/dL
- Males 40-75 years of age with ASCVD risk score between 7.5% - <20% and LDL-C 70-189 mg/dL
- Females 50-75 years of age with ASCVD risk score between 5% - <7.5% plus one risk enhancing factor and LDL-C 70-189 mg/dL
- Males 40-75 years of age with ASCVD risk score between 5% - <7.5% plus one risk enhancing factor and LDL-C 70-189 mg/dL
- Diabetics (females 50-60 or males 40-50 years of age) with LDL-C between 70-189 mg/dL and with ASCVD risk below 20%

When on the market, consumers will access the Web App through any device that has internet access. Once they access the site, they will have to answer a series of questions in order to qualify for treatment. If they qualify, they will enter an eCommerce environment where they will create a personal account and enter shipping and purchasing information. If they order drug, it will be shipped to them. Consumers will be able to purchase a limited supply (e.g., 45 or 90 days). Within a pre-specified window before their supply runs out, the consumer will be able to order additional drug through the Web App. However, before they can reorder, the Web App will ask them a limited number of health-related medical questions to ensure that they are still eligible for treatment. Consumers will also be asked to retest their cholesterol and enter their LDL-C into the app to ensure they are getting an adequate treatment effect.

Transactional emails will be sent to let them know the status of their drug orders, to remind them to retest and to take their medication daily. All customers receive transactional emails, which is a standard practice in an eCommerce environment. In-market, customers may also “opt-in” to receive additional reminders or health-related information.

To test our eCommerce approach and ensure that our approach helps to ensure the proper use of nonprescription rosuvastatin, the AUS will mimic, as much as possible in a clinical trial, the in-market setting. Subjects will see advertisements for participation in a study for a new

OTC/nonprescription medicine. If they are interested, they contact a Call Center for pre-screening and, if they qualify, receive a link to the Web App. Subjects will take the initial TASS assessment. If they receive an “OK to Use” outcome, they will be asked to contact the Call Center to set up a virtual visit to review their medical and medication history and laboratory and BP data. Subjects who receive an “Ask a Doctor” outcome may also be eligible provided they contact their doctor, retake the initial TASS assessment and confirm a doctor said it is OK to take Crestor OTC. Provided the participant does not have a significant contraindication to treatment (e.g., we learn that the participant is pregnant during Virtual Visit 1), they will be able to order a 45- or 90-day drug supply. All subsequent reorders are performed using the Web App, which requires them to confirm that they have had no significant changes to their medical and medication history. They will also be asked to retest their LDL-C and enter it into the Web App. Provided the participant meets the DFL criteria programmed into the Web App for continued use, they can reorder medication.

Because participants in the AUS will purchase nonprescription rosuvastatin calcium online, they will receive eCommerce transactional communications (emails) that one would expect to receive when making an online purchase. Transactional emails will be sent to participants during the trial to let them know the status of their orders, their eligibility to reorder, and to remind them to retest. Some transactional messages will be accompanied by secondary messages reinforcing DFL requirements (e.g., adherence reminders). There will be no “opt-in” options incorporated into this study. All participants in the AUS will have a similar eCommerce experience that will mimic, as much as possible, the in-market setting.

CCI

4.3 Justification for Dose

The 5 mg dose of rosuvastatin was chosen for nonprescription use because it has a safety profile comparable to placebo and is highly efficacious, lowering LDL-C between 40% to 50% in controlled clinical trials. The dose planned for this study is based off the intended dose for the OTC product CCI

4.4 End of Study Definition

A participant is considered to have completed the study if he/she has completed all phases of the study including Virtual Visit 2. Participants who discontinue with sufficient medical and medication history information and, when necessary, a verified LDL-C collected prior to stopping the study to determine a final use outcome and has not withdrawn from the study are also considered to have completed the study.

A 30-day follow-up phone call will be performed after study drug completion/discontinuation to assess participants status with regard to AEs. The study will end when the last phone call is completed.

5 STUDY POPULATION

The study population will include the following:

Description	# of Participants
All-comers population ages 20*-75 who self-report having concern about high cholesterol or heart health	Enrolled: 1,220
	Evaluatable**: At least 500 with a goal of 100 of limited literacy

* Females 20-49 will be recruited until fifty females under the age of 50 years complete the initial TASS assessment in the Web App. After this quota of fifty females under the age of 50 years old is met, the inclusion criterion will be revised to females 50-75 years old.

**Evaluatable means the participant completed Virtual Visit 2 or has sufficient medical and medication history information and, when necessary, a verified LDL-C collected prior to stopping the study to determine a final use outcome.

Prospective approval of protocol deviations to recruitment and enrollment criteria, also known as protocol waivers or exemptions, is not permitted.

5.1 Recruitment Strategy

An appropriate recruitment strategy is critical for any study to successfully complete with the right participant population. As technology and digital connectedness have increased over the years, most consumers have developed a “digital footprint.” This refers to the information about a particular person that exists on the internet as a result of their online activity. The potential to leverage this information for digital recruitment has grown.

During the All-comers Self-Selection study, the majority of participants met a “Do Not Use” criterion and were stopped from proceeding by the TASS. Only ~5% of the participants that completed the All-Comers SS study obtained an “Ok to Use” outcome. This was expected as the goal of this stand-alone Self-Selection study was to demonstrate that participants correctly identified if they had a “Do Not Use” condition and that TASS correctly stopped them from proceeding.

In the AUS, an all-comers population will also be recruited; however, only those who obtain TASS outcomes of “OK to Use” or “Ask a Doctor” and indicate the doctor gave them permission to use nonprescription rosuvastatin will be able to proceed to a purchase and use the product in an unsupervised OTC environment. Based on the recruitment metrics from the All- Comers SS study, it is expected that approximately 80,000 consumers will need to respond to our advertising and contact the Call Center for pre-screening into the AUS. As such, we intend to use the advantages that digital recruiting affords us to more efficiently

enroll the AUS. This will allow us to complete the study with sufficient participants to complete a robust statistical analysis.

By using a consumer's "digital footprint," advertising can be targeted more efficiently by knowing key pieces of information about a subject without directly asking for the information. Information such as age, gender, cardiac event history, or statin use can be utilized to present the advertisements specifically to those subjects. Leveraging this strategic approach in conjunction with traditional advertising will allow us to narrow the top of the recruitment funnel. At the same time, we can ensure we have not biased or influenced the subject by asking questions that might impact how they would complete the assessment in the Web App or how they would respond to the pre-screening process with the Call Center. It is important to note that we are advertising and targeting in a manner consistent with how we will advertise and target individuals in the real world when the product is launched.

Therefore, some of the tactics used in the recruitment learnings from the Self-Selection study will continue to be leveraged, such as digital advertising methods that include paid search, social media, and display advertising, traditional recruitment methods (e.g., radio, TV, print, community outreach) and supplemental methods (e.g., aggregation through existing networks and databases). However, we will also be targeting based on additional key information such as age, gender, cardiac events, and statin use which, as stated above, are similar methods that will be used when the product is commercialized.

Methods of recruitment may also include the following, which can be used alone or, in combination:

Digital	Traditional	Supplemental
Keyword Searches, Age, Gender, Topics/Interests, Audience based, Geographically based, Online Behavior, Retargeting (showing ads again in the future if a consumer showed interest in the study but did not call the Call Center).	Geographically based, Specific Channels, Specific Newspapers/Magazines, Specific Radio Stations	Age, Gender, Conditions, Geographically based

5.2 Inclusion Criteria

Participants are eligible to be included in the study only if all of the following criteria apply:

- 1 Males, 20-75 years of age.
- 2 Females, 20-75 years of age (This inclusion criterion will be applied until 50 females under the age of 50 years complete the initial TASS assessment in the Web App. After this quota of 50 women under the age of 50 years old is met, the inclusion criterion will be revised to women 50-75 years old).

- 3 Respond to advertising regarding a concern about high cholesterol or heart health.
- 4 Able to read speak and understand English.

Additional Criteria for Inclusion into Actual Use (at Virtual Visit 1)

- 1 Participant reads and signs the Informed Consent form.

5.3 Exclusion Criteria

Participants are excluded from the study if any of the following criteria apply:

Exclusion Criteria

- 1 The participant or anyone in their household is currently employed by any of the following:
 - A pharmacy or pharmaceutical company
 - A consumer healthcare company
 - A manufacturer of medicines
 - A managed care or health insurance company
 - A healthcare practice
 - An employee of AstraZeneca or Concentrics Research
- 2 The participant has ever been trained or employed as a healthcare professional (physician, nurse, nurse practitioner, physician assistant, pharmacist).
- 3 The participant has, or cannot recall whether he/she has, received an investigational therapy as part of a clinical trial in the previous twelve (12) months.
- 4 The participant is not willing to provide contact information.
- 5 Previous enrollment in the present study.
- 6 The participant has a mailing address in Alaska, or their mailing address is a Post Office (PO) Box.
- 7 The participant is not willing to complete an eDiary.
- 8 The participant is a woman of childbearing potential and is not following contraception guidelines or is not willing to follow contraception guidelines including practicing abstinence or using at least 1 of the following acceptable methods of birth control for at least 1 month prior to entry into the study and for 1 month after study completion: hormonal – oral, implantable, injectable, or transdermal; mechanical – spermicide in conjunction with a barrier such as a condom or diaphragm; intrauterine device; or surgical sterilization of partner.
- 9 The participant does not have access to the internet.

- 10 The participant does not have an email address or the ability to receive emails.
- 11 The participant responds to the Single Item Literacy Screener 2 (SILS2) question (Chew et al 2008) “How confident are you filling out medical forms by yourself?” with either ‘extremely’ or ‘quite a bit.’ (If the quota for normal literacy is met, but the limited literacy target is not met, the SILS2 exclusion will be used to help increase the percentage of limited literacy participants at Virtual Visit 1. Participants identified as normal literacy by Rapid Estimate of Adult Literacy in Medicine (REALM) testing at Virtual Visit 1 will not be excluded from entry into the treatment phase of the study.)
- 12 Inability to conduct interviews in a private location so that sensitive information about the participant or study would not be overheard by others not permitted to hear such information.

Additional Criteria for Exclusion from Actual Use (at Virtual Visit 1) Confirmation by CMOG clinician:

- 1 That the participant is pregnant, as determined by an approved self-administered OTC urine pregnancy test conducted for all female participants of childbearing potential (Female participants who are not post-menopausal or surgically sterile).
- 2 That the participant is breastfeeding.
- 3 That the participant has an allergy to rosuvastatin.

5.4 Lifestyle Considerations

No lifestyle restrictions are required for this study.

5.5 Pre-Screen Failures

Pre-screen failures are defined as all subjects who meet one of the following categories:

- Did not meet SS inclusion or met SS exclusion
- Qualified refused
- Received Web App link but did not complete the TASS assessment.
- Received Web App link and received a “Do Not Use” outcome.
- Received Web App link and received an “Ask a Doctor” outcome and did not go back into the Web App and indicate a doctor said it was okay to proceed.
- Received Web App link, received an “OK to Use” outcome or an “Ask a Doctor” outcome and indicated a doctor said it was okay to proceed but never created a Web App account.
- Received Web App link, received an “OK to Use” outcome or an “Ask a Doctor” outcome and indicated a doctor said it was okay to proceed, created a Web App account but did not make an initial purchase of study drug.

- Received Web App link, received an “OK to Use” outcome or an “Ask a Doctor” outcome and indicated a doctor said it was okay to proceed, created a Web App account, made an initial purchase of study drug but did not schedule their first visit.
- Received Web App link, received an “OK to Use” outcome or an “Ask a Doctor” outcome and indicated a doctor said it was okay to proceed, scheduled their first visit but did not sign ICF (either did not show for their first visit or showed but decided not to sign ICF).

Information on pre-screen failures will be reported. A minimal set of pre-screen failure information is required to ensure transparent reporting of pre-screen failure subjects to meet the Consolidated Standards of Reporting Trials (CONSORT) publishing requirements and to respond to queries from regulatory authorities. Minimal information includes demography, pre-screen failure details, and eligibility criteria ([Schulz et al 2010](#)).

Individuals who do not meet the criteria for participation in this study (pre-screen failures) may not be rescreened.

6 STUDY INTERVENTION

Study intervention is defined as any investigational intervention(s), marketed product(s), placebo, or medical device(s) intended to be administered to a study participant according to the study protocol.

6.1 Study Intervention Administered

6.1.1 Investigational Products

Table 2 Investigational Products

ARM Name	Crestor 5 mg
Intervention Name	Rosuvastatin calcium
Type	Combination product (Drug and SaMD)
Dose Formulation	Tablet
Unit Dose Strength(s)	5 mg
Dosage Level(s)	1 tablet once-daily
Route of Administration	Oral
Use	Lower Cholesterol, a key risk factor for heart disease.
IMP and NIMP	IMP

Sourcing	Drug provided centrally by the Sponsor through AstraZeneca iPR Pharmaceuticals Inc. manufacturing site Software provided by AstraZeneca through Idea Evolver
Packaging and Labelling	Study Intervention will be provided in 1 or 2 45-count bottles. Each bottle will be labelled as per CFR regulations.

6.1.2 Software as a Constituent Part

The proposed Web App is being developed as a constituent part of a combination product by a third-party collaborating closely with AstraZeneca.

The Web App features a TASS tool which allows consumers to answer a select set of health-related questions in order to determine consumer suitability for self-selection, purchasing, and ongoing administration and adherence of Crestor OTC (investigational product). Crestor OTC will only be available online for purchase via the Web App and direct shipment to the consumer. The TASS tool is a specific and critical “function” of the broader Web App. The TASS tool specifically utilizes an algorithm (i.e., decision tree and business logic aligned to the DFL and treatment guidelines) that operates on consumer data input to produce an outcome regarding the appropriateness of Crestor OTC treatment for the respective consumer. The broader Web App also includes additional components such as a welcome statement, privacy statement, account setup, shopping cart checkout, and account management, which are not considered medical device functions.

The TASS acts as a digitized, interactive version of the DFL, allowing consumers to answer a dynamic and personalized set of health-related questions, in lieu of browsing/searching a DFL for information pertinent to them. It also calculates a 10-year ASCVD risk based on the Pooled Cohort Equation (PCE) to determine consumer suitability for moderate-intensity statin treatment in accordance with the 2018 Treatment Guideline ([Grundy et al 2018](#)). Potential consumers are eligible to purchase Crestor OTC if they meet the requirements for safe use according to the DFL and have an appropriate calculated ASCVD risk score.

6.2 Preparation/Handling/Storage/Accountability of Interventions

- 1 A detailed process flow chart for product accountability has been developed (see [Appendix C](#)). The study product will be stored at a Central Depot to prepare the product and accompanying documentation (DFL, CIL, invoice/packing slip) for shipment via a delivery service. The study product will be stored in a secure and monitored area in accordance with the labelled storage conditions with limited access to only authorized staff. The Contract Research Organization (CRO) will work with the Central Depot to ensure only enrolled and investigator-approved participants will receive study product for the initial order. Provided the participant has no changes in health as administered via the Web App, subsequent reorders will automatically trigger shipment through the Web App

to the Central Depot immediately upon online purchase by the participant. Emails will also be used to inform participants when they should reorder. They will receive a reorder email at day 25 for a 45-day supply order and at day 45 for a 90-day supply order though the Web App will allow the participant to place another order after 5 days from the last order delivered date for the AUS. This will allow an assessment of participant behaviors around reordering of drug during the AUS to best position the appropriate ordering windows in-market.

- 2 The investigator is responsible for final drug accountability, reconciliation, and record maintenance (i.e., reconciliation and final disposition records).
- 3 Further guidance and information for the final disposition of unused study interventions are provided in the Product Accountability Log.

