Overall compliance with dosing will be assessed using three methods: pill count, diary review and number of reorders using the Web App. The first assessment for overall compliance uses the pill count or eDiary. Each participant will have overall compliance assessed and will be considered successfully compliant with dosing if they took between 50% and 120% of their pills. The target threshold for the overall compliance endpoint is an observed point estimate for the percentage of participants falling in the 50-120% range to be at least 50%. In other words, at least half of the participants need to be successfully compliant with dosing. In addition to overall compliance, a longitudinal compliance rate will be calculated to assess compliance with continuous dosing across each study drug reorder supply period. The pill use for this analysis will come from the eDiary. Finally, an additional assessment of longitudinal compliance/persistence will be performed using reorder data from the Web App. This endpoint will evaluate the percentage of users who were eligible for continuous treatment and ordered 180 days of therapy. To be eligible for continuous treatment, the participants must have received an “OK to Use” outcome or an “Ask a Doctor” outcome and indicate the doctor gave them permission to continue treatment, and they continued to have one of these outcomes at all assessments (initial, reorder and final use). Participants who discontinue or withdraw are not eligible for continuous treatment. Success is persistence $\geq 50\%$ similar to the other compliance/persistence endpoints. The rationale for setting the compliance/persistence thresholds at 50% is based on prescription data which shows that after 180 days only about 44% of people continue to refill their prescriptions. Our intention is to show that our approach will be at least as good, if not better, on compliance and persistence than what is observed in the real world ([IQVIA](#)). Additionally, assuming an individual takes the medicine intermittently for the duration of the study, a 50% dosing compliance would equate to taking a 2.5 mg dose of rosuvastatin compared to a 5 mg dose. Based on the clinical trial data, a 2.5 mg dose gives an LDL-C lowering of approximately 35% ([Olsson et al 2001](#)). Therefore, someone taking roughly half of their pills (e.g., a 45-pill count takes about 90 days to use) would still receive excellent efficacy.

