 - All participants at Virtual Visit 1 will be allowed to enter the use period of the study provided a CMOG clinician has not determined that the participant has a condition for which treatment would pose an unacceptable risk (e.g., allergy to rosuvastatin or a woman who is breastfeeding or pregnant).

Use Period

- 16 The use period of the study begins on the day that the product is delivered to the address provided by the participant. The use period lasts 6-months. During this period, participants have the option to purchase more product.
- 17 Participants will need to utilize the eDiary to record the unique bottle ID(s) received for this initial shipment and any subsequent reorder shipments received to confirm receipt of delivery of the study drug.

- 18 Participants will be instructed to use the eDiary to record when they took study drug, have changes to any medications and have any changes in health status. The diary will be reviewed for AEs by a CMOG clinician at the day 60 and day 120 phone call (phone calls described in Step 22 below) and at the Virtual Visit 2. AEs will be followed to resolution. See Section 8.1 for further details regarding eDiary.
- 19 The timing for reordering drug for a 45-day order and a 90-day order will be after 5 days from the date of last delivery. Emails will also be used to inform participants when they should reorder. They will receive a reorder email at day 25 for a 45-day supply order and at day 45 for a 90-day supply order. Participants will have a TASS assessment performed during the reorder. Provided they receive an “OK to Use” outcome or an “Ask a Doctor” outcome and indicate the doctor gave them permission to continue treatment, they can reorder. However, the participant does not interact with a CMOG clinician to have their medical and medication history assessed during reorders.

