- If, on the other hand, the CMOG becomes aware of a “Stop Use” criterion during the telephone call that the participant did not identify, all Virtual Visit 2 procedures except a participant TASS and study mandated test for LDL-C will be performed. The reason for not repeating the TASS is that the participant did not self-identify the “Stop Use” criterion. Instead, the CMOG identified the criterion and discussed with the participant, which could bias the participant’s behavior when completing the TASS. For example, a participant who did not realize they should have stopped drug because of severe muscle symptoms, may answer “yes” to this question in the TASS and be categorized as a correct selector when, in reality, they may have answered “no” to this question if they had not spoken to a CMOG clinician prior to completing the TASS. Because the study staff had to

inform the participant that they met a “Stop Use” criterion, they will be considered a failure when evaluating the second co-primary endpoint related to “use”.

- Participants who the CMOG clinicians identify as having experienced “Stop Use” criteria are considered “Discontinued from Study Intervention” and not a withdrawal (refer to Section 7.1). In general, the only events recorded in an eDiary or communicated to the study staff during a phone check that would result in study medical personnel instructing the participant to stop taking rosuvastatin are “Stop Use” criteria. If such a situation occurs, the participant will be classified as a discontinuation from study intervention due to “Adverse Event” or “Pregnancy” and scheduled for a Virtual Visit 2.

If a participant records a “Do Not Use” warning in their eDiary, we will not contact them. Our intent in the AUS is to keep interactions with the participants to a minimum so we do not influence the participant’s behaviors or bias the outcome of the study. By doing this, we allow the real-life behavior to continue into the next reorder, at which time, the TASS reorder assessment would result in a “Crestor OTC is no longer right for you” message along with a message to stop drug and contact a doctor. In the AUS, the participant will also be messaged to contact the call center to schedule Virtual Visit 2.

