$$\text{Longitudinal Compliance Rate (\%)} = \frac{100 * (\text{Number of participants with 50-120\% Supply Period Compliance across all supply periods})}{\text{Total number of participants in PP population for whom supply period compliance was assessed across all supply periods}}$$

Longitudinal Compliance Rate, along with the number of participants with 50-120% supply period compliance across all supply periods will be summarized by subgroup and overall on the PP population.

7 Percentage of participants who were persistent as determined by reorder data from the Web App will be calculated as follows:

$$\text{Percentage} = \frac{100 * (\text{Number of participants who were persistent})}{\text{Total number of participants eligible for continuous treatment}}$$

[figure not shown]
Persistence is defined as participants eligible for continuous treatment and delivered the full 180 days or more of treatment. The number and percentage of participants who were persistent will be summarized by subgroup and overall on the PP population and the AUS ITT population.

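### The reorder-based persistence endpoint counts 180 days of drug delivered without regard to when, so it does not measure continued use or refilling at 180 days and cannot be set against the 44% refill benchmark

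*Protocol*

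**What the plan says.** The definition is the same in Protocol 9.4.2.2 item 7 and SAP 4.2.3: "Persistence is defined as participants eligible for continuous treatment and delivered the full 180 days or more of treatment". The denominator is everyone eligible for continuous treatment, and success is an observed percentage of at least 50%, with no interval or test. The figure is to be shown for both the PP and the AUS ITT population, but the formula keeps the eligible-only denominator in each.

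Eligibility (SAP 3.2.9; Protocol 3.1) means a qualifying outcome at the initial, every reorder and the final use assessment. Anyone who discontinues or withdraws is not eligible.

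On ordering, Protocol 4.2 offers a choice of supply: "they will be able to order a 45- or 90-day drug supply". Protocol 6.2 says that "the Web App will allow the participant to place another order after 5 days from the last order delivered date", and Protocol Section 8, step 19, gives the same window for both sizes: "The timing for reordering drug for a 45-day order and a 90-day order will be after 5 days from the date of last delivery". Protocol 6.2 adds the prompts: "They will receive a reorder email at day 25 for a 45-day supply order and at day 45 for a 90-day supply order". The planned in-market rule is tighter: "Within a pre-specified window before their supply runs out, the consumer will be able to order additional drug through the Web App".

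Protocol 3.1 bases the 50% thresholds for compliance and persistence on "prescription data which shows that after 180 days only about 44% of people continue to refill their prescriptions", and states the aim of doing at least as well as real-world practice. That section describes the endpoint in terms of drug ordered, whereas 9.4.2.2 and the SAP use drug delivered.

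**The concern.** The benchmark is a statement about time: who is still refilling after 180 days. The endpoint is a running total that can be complete long before then, after which no further order is needed to keep the status. A participant could receive 180 tablets early, stop taking them without saying so, obtain a qualifying outcome at Visit 2 and be counted as persistent. Protocol 7.2 says that poor dosing compliance is not in itself a ground for withdrawal, so such a person need not leave the eligible group.

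Order size also changes what is tested. A 90-day orderer has one reorder decision to make and a 45-day orderer has three.

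At stake is the claim that persistence in this program matches or exceeds real-world prescription refilling. That claim would rest on an early delivery count in a selected group.

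**Working it through.** Neither document states the day on which 180 days of supply is reached, so there is no planned figure to reproduce.

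**Inputs**
- Orders needed: 180/90 = 2 (one reorder) or 180/45 = 4 (three reorders).
- Gap from one delivery to the next order: 5 days at the earliest, for either size; 45 days (90-day order) or 25 days (45-day order) if the email is acted on. I count the email day from delivery of that order.
- First delivery: Day 1 (Protocol Section 8, step 15). The Schedule of Activities puts it at Day 0.
- Shipping time *s*: not given; assumed 0 to 5 days per order.

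**Formula:** day of the completing delivery = first delivery day + (orders − 1) × (gap + *s*).

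| Pattern | 90-day orders | 45-day orders |
|---|---|---|
| Earliest permitted | 1 + 5 = 6 to 1 + 10 = 11 | 1 + 3×5 = 16 to 1 + 3×10 = 31 |
| Each email followed | 1 + 45 = 46 to 1 + 50 = 51 | 1 + 3×25 = 76 to 1 + 3×30 = 91 |
| At run-out, *s* = 0 | 1 + 90 = 91 | 1 + 3×45 = 136 |

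Counting from Day 0 lowers each entry by one, so the email row starts at Day 45 and Day 75. Reading the window as a six-day gap, counted from Day 0, gives 6 to 11 for 90-day orders and 3×6 = 18 to 3×11 = 33 for 45-day orders. The ranges are therefore about Day 6-11 and Day 16-33 at the earliest, and about Day 45-51 and Day 75-91 by email. Other combinations of the two conventions move the earliest dates by a day.

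**Time left after the criterion is settled, if emails are followed:** 180 − 51 = 129 to 180 − 45 = 135 days (90-day orders); 180 − 91 = 89 to 180 − 75 = 105 days (45-day orders). The earliest possible reorderer has 180 − 6 = 174 days left.

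**Threshold against benchmark.** Protocol Table 3 plans for 1,000 entering the use phase and 500 evaluable. The evaluable group includes some who discontinued with enough history, so on these figures at most 500 are eligible for continuous treatment. I assume the 44% refers to all who start a prescription; the documents do not give its denominator.

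| Eligible (assumed) | 50% target as a share of 1,000 | Persistence among eligible needed to equal 44% of 1,000 (440) |
|---|---|---|
| 500 | 250/1,000 = 25% | 440/500 = 88% |
| 450 | 225/1,000 = 22.5% | 440/450 = 97.8% |
| 400 | 200/1,000 = 20% | 440/400 = 110%, not attainable |

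**The case against.** **Month 6.** A reader might infer that the endpoint says nothing about month 6. The documents do not support that. A participant who discontinues, withdraws or lacks a qualifying final use outcome cannot count as persistent, and for those with an OK to Use outcome at each reorder the final assessment takes place at the end of the six months. This stands. But those people leave the denominator as well, so their loss does not lower the percentage.

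**The early window.** It is deliberate: Protocol 6.2 says that it is there to observe reordering behavior and help set in-market windows. Nor is it the root cause, since run-out ordering also settles delivery well before Day 180. Both points stand. They justify the ordering rule but not an undated endpoint built on it.

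**Companion endpoints.** Compliance is judged in three ways. With an intended duration of 180 days and one tablet a day, stopping at Day 50 gives a pill-count compliance of 50/180 = 27.8%, a failure. The eDiary measure requires 50-120% in every supply period and treats missing entries as missed doses, so a 90-day orderer who stops at Day 50 scores zero in period 2. This protection is real but incomplete: 90 tablets and then none gives 90/180 = 50%, a pass on pill count. The eDiary endpoint would catch that person, but persistence has its own 50% target and would still count them.

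**Order size.** Results are already planned by order preference (Protocol 9.4.1.1; SAP 4.1.2). That displays the difference between one and three reorder decisions but does not remove it.

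**Do Not Use events.** Protocol 8.1 says of these that "we allow the real-life behavior to continue into the next reorder", and a reader might infer that this contradicts the early reorder window in 6.2. It does not: neither passage says that a further reorder must fall due before Visit 2. A participant whose last order was OK to Use completes a final assessment at Visit 2 (Protocol Section 8, step 25), so the event is still scored.

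**Conclusion.** The concern holds in a limited form. As defined, persistence shows that enough drug for 180 days reached participants who also stayed eligible to the end. It does not estimate continued use or refilling at 180 days and should not be compared with the 44%.

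The undated definition and the eligible-only denominator are plain in both documents. The calendar figures rest on assumed shipping of 0 to 5 days. The email-based figures further assume that participants act on each email; the documents give no expected reorder times. The 25% and 88% figures rest on Table 3's planning numbers and on my reading of the benchmark's denominator.

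The reach is limited to one of three secondary dosing endpoints, with a point-estimate target and no hypothesis test. The co-primary endpoints are unaffected. The change is worth making because the target is a stated success criterion and the data for a better measure are already collected.

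**What to change.** In Protocol 9.4.2.2 item 7 and SAP 4.2.3:

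1. Keep delivery-only persistence as a reported figure. Show with it the day on which 180 tablets was reached, and split it by first order size.
2. Add a dated measure: 180 or more days delivered and eDiary-recorded dosing in the last 30 days before Visit 2. State in advance how much recorded dosing counts, since a single tablet would be a weak test. Do not allow a pill-count fallback, because an end-of-study total cannot date doses.
3. Report the dated measure also with all AUS ITT participants in the denominator, counting discontinuations and withdrawals as non-persistent.
4. Base any statement against the 44% benchmark on the AUS ITT version only, and align Protocol 3.1 with that. Use one term, ordered or delivered, throughout.

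The ordering rule need not change. No new data are needed: delivery dates are recorded (Protocol 6.4; Appendix C), and the eDiary captures date, time and amount taken (Protocol 8.1). The cost is wording in both documents; if only the SAP is changed, the addition belongs in SAP Section 7. The downside is a lower persistence figure, with participants who did not keep the eDiary counted as not persistent.
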